6.1.3.2. ITT and PP Populations

As a supportive analysis, the primary MMRM analysis will be repeated using both the ITT and PP populations. In addition, the ANCOVA model after MI will also be repeated for ITT population. The baseline time to stand from supine (<5 seconds, ≥ 5 seconds) will be included in the testing model in the ITT analysis.

6.1.3.3. *Modification of mITT Criteria (+/- 15%)*

As supportive analyses, separate MMRM models similar to the primary analysis will be used to evaluate the change in 6MWD from baseline to Week 72 for all subjects with a baseline 6MWD ≥ 255 meters (ie, -15% from the 6MWD ≥ 300 meter lower bound) or baseline 6MWD ≥ 345 meters (ie, +15% from the 6MWD ≥ 300 meter lower bound)) and who also meet the age and stand from supine criteria for the mITT population (ie, 7 to 16 years old and time to stand from supine ≥ 5 seconds at baseline).

6.1.3.4. *Checking Missing at Random Assumption*

For the primary analysis, an additional sensitivity analysis will be employed to check the MAR assumption underlying the MMRM model where the reason for drop-out is considered. Subjects with following discontinuation reasons will be imputed using MI method using subjects in placebo arm who completed double-blind period of the study without missing values.

- Adverse event
- Withdrew consent
- Investigator decision

This analysis will be performed for mITT population. Detailed method and SAS codes are described in [Appendix 3](#).

6.1.3.5. *Using Average of Day 1 and Day 2 6MWDs Rather than Maximum*

The primary analysis uses the maximum of valid Day 1 and Day 2 6MWDs for baseline and Week 72. As a sensitivity analysis, the same analysis will be repeated with the average of valid Day 1 and Day 2 6MWDs for baseline and Week 72 for mITT population. For this analysis, the actual week for Baseline and Visit 8 will be calculated based on the first day of the visit.

6.1.3.6. *Assess the Impact of COVID19*

To assess the impact of COVID19, a sensitivity analysis will be performed similarly to the primary MMRM analysis and ANCOVA analysis after MI by removing all COVID19 impacted visits (as collected on CRF) for mITT and ITT populations. The baseline time to stand from supine (<5 seconds, ≥ 5 seconds) will be included in the testing model in the ITT analysis.

6.1.3.7. *Assess the Impact from Potential Correlation among Siblings*

In this study, brothers participating in the study will receive the same treatment group designation to minimize potential compromise of the study drug blinding and to reduce the chance of dosing errors within families. In the primary analysis, siblings will be considered as independent subjects. However, the assessments from two or more brothers may be highly correlated. To assess the impact of potential correlation among siblings, the primary MMRM analysis will be repeated by including only data from the first sibling for mITT and ITT populations. The baseline time to stand from supine (<5 seconds, ≥ 5 seconds) will be included in the testing model in the ITT analysis.

6.1.3.8. *Non-parametric analysis*

As a sensitivity analysis, the change from baseline at Week 72 in 6MWD using observed data between two treatment groups will be compared using Wilcoxon rank sum test stratified by baseline concomitant corticosteroid type (deflazacort, prednisone/prednisolone) and baseline 6MWD category (<300 meters, 300 to <350 meters, 350 to <400 meters, \geq 400 meters) for mITT population.

6.1.3.9. *Subgroup Analysis*

The change from baseline in 6MWD will be summarized by visit for subgroups below for mITT and ITT populations:

- Region (North and Latin America, Europe, Asia Pacific)
- Stop codon (UAA, UAG, UGA)

In addition, the change from baseline in 6MWD will be summarized at each post-baseline visit for the following subgroups based on baseline disease severity for ITT population:

- Baseline disease severity
 - Baseline 6MWD <300 meters
 - Baseline 6MWD \geq 300 meters, time to rise from supine \geq 5 seconds at baseline, and 7 to 16 years old
 - Baseline 6MWD \geq 300 meters and time to rise from supine <5 seconds at baseline, or baseline 6MWD \geq 300 meters, time to rise from supine \geq 5 seconds at baseline, and younger than 7 or older than 16 years old

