4.3 Randomization and Stratification

After a subject has completed all screening and baseline assessments and has been confirmed to be eligible by the investigator in accordance with the inclusion and exclusion criteria, the subject can be randomized into the study.

In order to obtain a treatment arm assignment for a subject, a site representative will access the IRT system. The user will need to supply the IRT system with at least the following information so that the system can assign the subject to a treatment group.

- Site number as previously assigned by PTC Therapeutics
- Subject number as previously entered into the IRT system
- Subject initials

- Subject date of birth
- Type of corticosteroid
- Results of the baseline Day 1 and Day 2 6MWTs in meters
- Result of the baseline time to stand from supine in seconds
- Brother already randomized into the study: yes or no; if yes, subject number of the previously randomized brother
- Subject's weight at baseline in kg

The IRT system will provide instructions for dispensing study drug (see Section 5.1.4).

Subjects will be randomized in a 1:1 ratio to 1 of 2 possible treatment assignments:

- Placebo
- Ataluren (10, 10, 20 mg/kg)

In order to balance treatment allocation by potentially important predictive factors for the 6MWT, the following stratification factors will be used:

- Type of concomitant corticosteroid use at baseline: (deflazacort versus prednisone/prednisolone)
- Maximum of the Day 1 and Day 2 6MWTs performed at baseline: <300 meters versus ≥ 300 to <350 meters versus ≥ 350 to <400 meters versus ≥ 400 meters
- Time to stand from supine at baseline: <5 seconds versus ≥ 5 seconds

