11.3.3 Blinding

Double-blind administration of study treatments is utilized to provide additional and substantial protection against motivational bias on the part of subjects, caregivers, clinic staff, and other study personnel, with respect to assessment of efficacy and safety parameters.

Several steps have been taken in the proposed protocol design to minimize the prospect of systematic unblinding. Placebo is available that is an excellent match for both unmixed and mixed ataluren in terms of appearance, texture, taste, and odor. Brothers participating in the study will receive the same treatment group designation to minimize potential compromise of study drug blinding and to reduce the chance of dosing errors within families.

Packaging and labeling is identical for both the active drug and placebo. Blinding will be done centrally rather than at sites. Access to randomization information during the course of the study will be restricted to the IRT system CRO. The focus of the interim safety reviews will be on blinded data without segregation by treatment group. The final unblinded analysis of the randomized phase of the study will only be performed when the data set is complete, and a snapshot has been frozen and archived.

Unblinding in individual subjects who experience AEs is rarely required to provide effective intervention and support. Thus, disincentives for unblinding for AEs are included in the study. Investigational personnel will not have access to information at the site that would permit unblinding, and the individual subject randomization codes will only be obtainable through an auditable process involving the IRT system. Clinic staff will be made aware that such unblinding will preclude a subject from continuing with study drug administration. Unblinding will also require discussion between the investigator and the PTC Therapeutics medical monitor; this provision is not intended to prevent an investigator from proceeding with unblinding, but to ensure that appropriate consultation is obtained, that the investigator is aware of the consequences of the unblinding for the subject's continued participation in the study, and that appropriate permission is granted to the IRT system to release the treatment assignment only for that subject.

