2.4. Sample Size

The hypothesis of this study is that the slope of change in 6MWD from baseline to Week 72 (end of double-blind treatment period) will be 1.0 meter/week better in the ataluren arm than in the placebo arm, within a subset of subjects who are ≥ 7 to 16 years old with baseline 6MWD ≥ 300 meters and baseline time to stand from supine ≥ 5 seconds. The baseline 6MWD is defined as the maximum of the 6MWDs from a valid 6MWT on Day 1 and Day 2. Similarly, the Week 72 6MWD is defined as the maximum of the 6MWDs from a valid 6MWT on Day 1 and Day 2 of the Week 72 visit (end of double-blind treatment period). With a 1:1 randomization, 154 subjects will be required (77 subjects in the ataluren treatment arm and 77 subjects in the placebo arm) to detect a difference of 1.0 meter per week between ataluren and placebo with 85% power (two-sided $\alpha = 0.05$), assuming a common standard deviation of 2.058 meters per week. Further assuming a premature discontinuation rate of $\sim 5\%$, a total of 162 subjects (81 subjects in the ataluren treatment arm and 81 subjects in the placebo arm) will be enrolled for the primary endpoint analysis. The study is expected to enroll ~ 340 subjects overall, including those outside of the primary analysis population.

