6.1.2. Primary Analysis

The rate of change in 6MWD over 72 weeks (slope) in the mITT population will be considered as the primary efficacy endpoint.

A MMRM model will be employed using a random intercept and a random slope of change per week using observed data assuming the missing assessments are MAR. The slope will be compared between ataluren and placebo, and the estimated treatment difference with corresponding 95% confidence interval (CI) will be provided. The estimated difference in the change at Week 72 will also be provided to facilitate interpretation. The MMRM model will include baseline concomitant corticosteroid type (deflazacort, prednisone/prednisolone), baseline 6MWD category (<300 meters, 300 to <350 meters, 350 to <400 meters, ≥400 meters), baseline 6MWD, treatment, week (actual week at the visit as a continuous variable), the interaction of week and baseline 6MWD, and the interaction of week and treatment. The unstructured covariance matrix (UN) will be used in the MMRM model. Other types of covariance matrix (heterogenous Toeplitz, Toeplitz, and compound symmetric) will be explored in the case of non-convergence of UN. For this analysis, any subjects who lose ambulation during the study will be assigned a 6MWT result of 0 meters for the first visit in which the subjects lose ambulation and set for missing for all visits afterwards while they participate in the study.

The primary endpoint will be tested at the significance level of 0.05 (two-sided). If $p < 0.05$, then the primary endpoint will be considered statistically significant, and the study will be declared positive.

The example SAS code is listed below:

```
PROC MIXED data=<dataset> method=reml;  
  CLASS Cortico Subjid Trt C6WMD;  
  MODEL N6WMD = Cortico C6WMD Trt B6WMD Week Week*B6WMD  
    Week*TRT/S CL;  
  RANDOM Int Week/type=un subject=Subjid;  
  LSMEANS TRT / pdiff at Week=72 CL;  
RUN;
```

where

N6WMD = 6WMD at each visit (Baseline to Week 72)

B6WMD = Baseline 6WMD
C6WMD = Baseline 6WMD category
Cortico = Baseline concomitant corticosteroid type
Week = Actual study week at each visit
Trt = Treatment group
Subjid = Subject
Int = Intercept

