3.1.2. Supportive/Sensitivity Analyses

To confirm the robustness of the conclusions from the analyses performed on the ITT analysis set additional sensitivity analyses were added as detailed below.

3.1.2.1. *Analysis of Covariance (ANCOVA) Using Multiple Imputation (MI)*

The ANCOVA analysis using MI that was prespecified in SAP for the double-blind portion of Study 041 is still considered as a sensitivity analysis based on ITT population.

3.1.2.2. *Checking Missing at Random Assumption*

An additional sensitivity analysis is planned to check the MAR assumption underlying the MMRM categorical model where the reason for drop-out is considered based on ITT population. Subjects with following discontinuation reasons are to be imputed with MI method using subjects in placebo arm who completed double-blind period of the study without missing values.

- Adverse event
- Withdrew consent
- Investigator decision

3.1.2.3. *Using Average of Day 1 and Day 2 6MWDs Rather than Maximum*

The primary analysis uses the maximum of valid Day 1 and Day 2 6MWDs for baseline and Week 72 visits. As a sensitivity analysis, the same analysis is to be repeated with the average of valid Day 1 and Day 2 6MWDs for baseline and Week 72 visits for ITT population.

3.1.2.4. *Assess the Impact of Coronavirus Disease of 2019 (COVID19)*

To assess the impact of coronavirus disease of 2019 (COVID19), a sensitivity analysis is planned similar to the MMRM categorical analysis and ANCOVA analysis after MI by removing all COVID19 impacted visits (as collected on CRF) for ITT population.

3.1.2.5. *Assess the Impact from Potential Correlation among Siblings*

In this study, brothers participating in the study received the same treatment group designation to minimize potential compromise of the study drug blinding and to reduce the chance of dosing errors within families. In the primary analysis, siblings are considered as independent subjects. However, the assessments from two or more brothers may be highly correlated. To assess the impact of potential correlation among siblings, the MMRM categorical analysis are to be repeated by including only data from the first sibling for ITT population.

3.1.2.6. *Non-parametric analysis*

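### Brothers share a treatment arm but are analysed as independent; if their outcomes are positively correlated, the primary standard error is somewhat too small, and the planned sibling check covers only the 6MWD MMRM

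*SAP*

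**What the plan says.** Protocol 11.3.3 (Blinding): "Brothers participating in the study will receive the same treatment group designation". The reasons given are protection of the blind and fewer dosing mix-ups at home. Protocol 4.3 has the site tell the IRT whether a brother is already in the study and, "if yes, subject number of the previously randomized brother".

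Double-blind SAP 6.1.3.7: "In the primary analysis, siblings will be considered as independent subjects". It then acknowledges possible high correlation between brothers and plans to rerun the primary MMRM with only the first sibling, in mITT and ITT. The document on changes from the planned analysis (3.1.2.5) keeps both elements: "siblings are considered as independent subjects", with a first-sibling rerun of the categorical MMRM in ITT.

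The example code for the primary model (double-blind SAP 6.1.2) and for the categorical model (change document 3.1.1) identifies correlation by subject only. Neither contains a family term. The sample size section (double-blind SAP 2.4) makes no allowance for siblings.

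**The concern.** A later brother's arm is fixed by his brother's allocation, so in those families the family is the unit of allocation. Two positively correlated boys in one arm carry less information about that arm's mean than two unrelated boys. A model that ignores this understates the variance of the treatment difference, narrows the confidence interval and lowers the p-value.

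At stake is the confirmatory decision, which the SAP ties to that one p-value: "The primary endpoint will be tested at the significance level of 0.05 (two-sided"). Both key secondary endpoints, the TFT composite and rNSAA, sit behind it in the fixed sequence and rest on the same independence assumption. So do the 6MWD ANCOVA, the Cox models and the inferential analyses of the open-label SAP, and none of these has a sibling analysis.

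**Working it through.** **1. The plan's own figure.** Inputs from double-blind SAP 2.4: the sample size is chosen "to detect a difference of 1.0 meter per week between ataluren and placebo with 85% power", "assuming a common standard deviation of 2.058 meters per week"; alpha is 0.05 two-sided, allocation 1:1.

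n per arm = 2 x (1.960 + 1.036)^2 x 2.058^2 / 1.0^2 = 76.05, rounded up to 77, so 154 in total. This matches the SAP. Power at 77 per arm is 85.4% (normal approximation) or 85.0% (noncentral t). The calculation assumes 154 independent boys.

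**2. Design effect.** Let an arm have n boys with outcome variance s^2, and let a share f of them be in same-arm brother pairs with correlation rho. There are fn/2 pairs, so

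Var(sum) = n s^2 + 2 x (fn/2) x rho x s^2 = n s^2 (1 + f rho).

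With the same f in both arms, the variance of the treatment difference is multiplied by DE = 1 + f rho. Then:
- understatement of SE = 1 - 1/sqrt(DE)
- actual two-sided alpha = 2 x [1 - Phi(1.96/sqrt(DE))]
- largest unadjusted p-value that stays significant after correction = 2 x [1 - Phi(1.96 x sqrt(DE))]

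This is a two-sample approximation to the slope comparison. A t-test simulation with 77 per arm agreed with it: 4 pairs per arm (f about 10%) and rho 0.5 gave 0.056.

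**3. Assumed range.** The documents state neither f nor rho, so every row is an assumption.

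| f | rho | DE | SE understated | actual alpha | p must be below |
|---|---|---|---|---|---|
| 2% | 0.3 | 1.006 | 0.3% | 0.051 | 0.049 |
| 5% | 0.5 | 1.025 | 1.2% | 0.053 | 0.047 |
| 10% | 0.5 | 1.050 | 2.4% | 0.056 | 0.045 |
| 10% | 0.7 | 1.070 | 3.3% | 0.058 | 0.043 |
| 15% | 0.7 | 1.105 | 4.9% | 0.062 | 0.039 |

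At N = 154, f = 10% is about 8 pairs in total. With rho 0.5, a correctly adjusted analysis would have about 83.7% power.

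**4. Cost of the first-sibling run.** Dropping one boy from each of 8 pairs leaves 146 boys (73 per arm) and about 83.5% power. With 2 pairs, power is about 85.0%.

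**5. The mITT slope result.** Table 1 of the change document gives 9.95 m (SE 14.9): z = 9.95/14.9 = 0.67, p about 0.50. Enlarging the SE by sqrt(1.105), the worst row above, gives p about 0.53. The conclusion is unchanged.

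**The case against.** The SAP raises the issue itself and pre-specifies an answer. One boy per family removes within-family correlation, so the first-sibling run gives a valid standard error for the 6MWD MMRM and would expose any material distortion. This stands. It is a sound check, and its cost is some power. The boys it drops are enrolled boys who were not independently randomised.

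The size is also unknown and probably small. The relevant rho is that of residual change after adjustment for baseline 6MWD, its category and corticosteroid type, not of raw walking distance. Brothers usually differ in age, and the protocol (11.2.3) notes that 6MWD tends to rise up to age 7 and fall afterwards. In mITT, a pair counts only if both boys meet the age, 6MWD and stand-from-supine criteria. All of this stands and argues for the lower part of the range.

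A reader might infer that the standard error is certainly too small and that every secondary endpoint is affected. The documents do not support that. They speak only of possible correlation and give no pair count. Safety and loss of NSAA items are secondary endpoints reported as tabulations, with no inferential standard error to distort.

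The objection does not dispose of the coverage gap. A sensitivity run leaves the decisive p-value unchanged, and it is specified for one model on one endpoint.

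**Conclusion.** The point holds, conditionally. If brothers' residual changes are positively correlated, the primary MMRM and the other inferential efficacy models understate the standard error by a factor of 1/sqrt(1 + f x rho). For assumed f of 2% to 15% and rho of 0.3 to 0.7, that is about 0.3% to 5%, with actual alpha about 0.051 to 0.062. These figures assume pairs rather than larger sibships, and a similar f in both arms.

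It would be wrong to conclude that this undermines the mITT finding: that result is non-significant, and a larger standard error only moves it further from significance. The exposure is an ITT p-value a little under 0.05, in the analysis (N=359) that the change document later names as the primary analysis of interest. The ITT result is not in these documents, so whether it is exposed cannot be judged here.

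The remaining defects are that the sibling check does not reach the key secondary endpoints, the ANCOVA, the Cox models or the open-label SAP, and that the term first sibling is not defined. The latter leaves it unclear what happens when both brothers are in ITT but only one is in mITT. This should be corrected, but it does not invalidate the trial.

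**What to change.** - Derive a family identifier from the sibling link in the IRT and keep all boys in the analysis.
- In the primary and key secondary MMRM and ANCOVA models, make family the top-level cluster with subject nested within it. Use either a family-clustered sandwich variance or family random effects. In the slope models the random effects must include a family-by-week term, because a family intercept alone does not address correlated slopes.
- Use a family-aggregated robust variance in the Cox models, and apply the same handling to the inferential analyses in the open-label SAP.
- Report the number of brother pairs by arm and analysis population.
- Define first sibling (for example, first randomised) within each analysis population, and keep that run as a sensitivity analysis.

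Cost: SAP wording and programming across several model types, but no new data. Confidence intervals would be slightly wider and p-values slightly larger. With few pairs, the family variance component may be estimated as zero; the sandwich variance is then the fallback. The multiple imputation behind the ANCOVA runs by arm without family structure, which should be stated as a limitation.

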6.2. Secondary Efficacy Variables

6.2.1. Key Secondary Efficacy Variables

6.2.1.1. *Timed Function Tests - Composite Scores*

The rate of change over 72 weeks (slope) in composite TFT scores will be considered as the first key secondary efficacy endpoint. The composite TFT scores will be defined as the average in times to run/walk 10 meters, climb 4 stairs, and descend 4 stairs. The change in composite TFT scores will be analyzed using the same MMRM model used for the primary analysis with factors of baseline concomitant corticosteroid type (deflazacort, prednisone/prednisolone), baseline 6MWD category (<300 meters, 300 to <350 meters, 350 to <400 meters, \geq 400 meters), treatment, visit, the average time in the three timed function tests at baseline, interaction of visit and treatment, and the interaction of week and baseline average time. The slope will be compared between ataluren and placebo, and the estimated difference in the change at Week 72 will also be provided to facilitate interpretation.

Subjects who cannot perform a timed function test within 30 seconds, including those who is LoA or the timed function test is above 30 seconds, will be assigned a value of 30 seconds for the respective test for calculating the average change in times. Similarly to the primary analysis, if the average time of the 3 TFT tests is 30 seconds for multiple visits for a subject, the 30 seconds will be kept for the first visit with the assessment of 30 seconds, and set for missing for all visits afterwards.

If the test of the primary endpoint is statistically significant, then this key secondary endpoints will be tested at the 0.05 (two-sided) significance level.

As supportive analyses, the same analysis will be repeated:

- ANCOVA based on mITT population after MI
- MMRM model based on ITT population with additional factor of the baseline time to stand from supine (<5 seconds, ≥ 5 seconds) in the model
- ANCOVA based on ITT population after MI (with additional factor of the baseline time to stand from supine (<5 seconds, ≥ 5 seconds) in the model)

The change from baseline in composite average of timed function will be summarized by visit for mITT and ITT populations, and for subgroups below for mITT and ITT populations:

- Region (North and Latin America, Europe, Asia Pacific)
- Stop codon (UAA, UAG, UGA)

In addition, the change from baseline in composite average of timed function will also be summarized at each post-baseline visit for ITT population for the following subgroups:

- Baseline disease severity
 - Baseline 6MWD <300 meters
 - Baseline 6MWD ≥ 300 meters, time to rise from supine ≥ 5 seconds at baseline, and 7 to 16 years old
 - Baseline 6MWD ≥ 300 meters and time to rise from supine <5 seconds at baseline, or baseline 6MWD ≥ 300 meters, time to rise from supine ≥ 5 seconds at baseline, and younger than 7 or older than 16 years old

